
	Dosing Period					
	4	5	6	7	8	9
Visit	W0	W0	W0	W1	W2	W3
Study Week						
Procedures	D1	D2	D4	D8	D15	D22
Study Day						
Visit window (days)	0	0	0	±1	±2	±2
Pregnancy test ^a	X	X	X	X	X	X
Physical examination (symptom-driven)	X ^b					
Vital signs ^c	X		X		X	X
12-lead ECG ^d	X		X	X	X	X
Haematology & eosinophils ^f	X	X ^m	X ^m	X	X	
Blood chemistry ^g	X				X	
Urinalysis	X				X	
FeNO	X	X ⁿ	X ⁿ	X	X	
Pulmonary Function Tests (Spirometry) ^e	X			X	X	
Total IgE	X				X	
C-reactive protein	X				X	
Biomarkers ^j	X				X	
Future analysis of additional cytokines	X				X	
Flow cytometry ^l	X				X	
CGI-C and ACQ-7 ^h					X	
Serum for PK ⁱ	X	X	X	X	X	X
Serum ADA and NAb (immunogenicity)	X					
Randomization	X					
UBP-101 administration/post-dose observation	X					
COVID-19 protocol as per site SOPs	X	X	X	X	X	X
Admission (Ad) or Discharge (Di) from site	Di					
Subject contact ^k	(X)		(X)		(X)	
Concomitant medication	X	X	X	X	X	X
Assess injection site reactions	X	X	X	X		
Review/Record AEs	X	X	X	X	X	X

Admission days are highlighted in light gray and dosing days in dark gray.

Table 6 Schedule of Events - Cohorts with █ Dosing Interval

Visit	Dosing Period					Observation Period										
	10	11	12	13	14	15	16	17	18	19	20	21	22	23	24	25
Study Week	W3	W4	W5	W7	W8	W8	W8	W9	W10	W11	W12	W16	W20	W24	W28	W32
Procedures																D225/ Final Visit
Study Day	D28	D29	D36	D56	D57	D58	D60	D64	D71	D78	D85	D113	D141	D169	D197	
Visit window (days)	±2	±2	±1	±2	±2	0	0	±1	±2	±3	±3	±5	±5	±5	±5	±5
Pregnancy test ^a	X	X	X	X	X	X	X	X	X	X	X	X	X	X	X	X
Physical examination (full)																X
Physical examination (symptom-driven)	X ^b	X ^b	X ^b	X ^b	X ^b	X ^b	X ^b	X ^b	X ^b	X ^b						
Body weight																X
Vital signs ^c	X	X	X	X	X	X	X	X	X	X	X	X	X	X	X	X
12-lead ECG ^d		X	X		X		X	X	X		X	X	X			X
Haematology & eosinophils ^f		X	X		X				X		X	X	X	X	X	X
Blood chemistry ^g		X	X		X				X		X	X	X			X
Urinalysis		X	X		X				X		X	X	X			X
Total IgE			X								X	X	X	X	X	X
C-reactive protein		X			X						X	X	X	X	X	X
FeNO		X			X						X	X	X	X	X	X
Pulmonary Function Tests (Spirometry) ^e		X			X						X	X	X	X	X	X
Biomarkers ^j		X			X						X	X	X	X	X	X
Future analysis of additional cytokines		X			X						X	X	X	X	X	X
Flow cytometry ^k		X			X						X	X	X	X	X	X
CGI-C and ACQ-7 ^h	X			X							X	X	X	X	X	X
Serum sample for PK ⁱ		X			X	X	X	X	X	X	X	X	X	X	X	X
Serum ADA and NAbs (immunogenicity)		X			X						X	X		X		X
Study drug administration		█			█											

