5.8 Safety Review Committee

5.8.1 General Safety Monitoring

Results of the SAD study performed with UPB-101 were reported in Section 1.4.1. In that clinical study, UPB-101 was safe and well-tolerated. Since the highest dose administered in the completed single-dose Phase 1 was [redacted] mg/kg (the equivalent of approximately [redacted] mg), all 3 doses proposed for Cohort 1 ([redacted]) and Cohort 2 ([redacted]) as well as the 2 doses of Cohort 3 ([redacted]) in the current study are supported by those data. However, the SRC will meet before the first subject in any cohort with [redacted] dosing receives their third dose as an extra precaution so as to assure that formal reviews of all the available safety data occur at specific timepoints in the study.

Part A: Subjects in Cohorts 1 and 2 will receive 3 doses of study drug. Before the first subject in each of those cohorts receives their third dose, the SRC will be convened. The committee will review at each of the 3 meetings the safety data available at that point in time from all enrolling cohorts. Subjects enrolled in Cohort 3 will receive 2 doses of the study drug. Therefore, no SRC meetings will be directly linked to the progress of those cohorts. The blinded safety data reviewed will include AEs, vital signs, physical examinations, ECGs, haematology, biochemistry, urinalyses, as well as subject withdrawals and replacements. Eosinophil data will not be sent to sites or reviewed by the SRC. Following this data review, the SRC will report their safety findings and make a recommendation whether the third dosing in the current cohort should proceed as planned or be modified (e.g., repeated or reduced), paused, or halted (Section 5.9 and Section 4.11).

Part B: Study drug exposures in Cohorts 4 and 5 will not exceed the exposure of any of the cohorts in Part A. If a [redacted] dosing regimen is selected for Cohorts 4 or Cohort 5 an SRC meeting will be convened prior to the first subject in the relevant cohort(s) receiving their third dose. The data to be reviewed, and the process for the SRC to report their safety findings, will be as those detailed for Part A above.

The data will be blinded for review; however, if considered necessary, the SRC can request that data be unblinded for either individual subjects or the entire dose cohort. The randomization code will be broken following tranScrip's standard procedures.

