7.2.4 Cohorts with █ Dosing Intervals

In cohorts with █ dosing intervals, study drug will be administered on Days █ for a █-week Dosing Period, except for Cohort 4 where study drug will be administered on Day 1 ONLY. None of the cohorts with █ dosing are dependent upon the SRC recommendations.

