### 10.12.1. *Injection Site Reactions*

For each injection site, information will be collected on whether any reactions are experienced by the subject. The number of subjects that ever experienced each of the reactions (pain, localised swelling, tenderness and erythema) will be summarized by treatment group, as well as the maximum severity experienced for each of the symptoms. Additionally, the number of subjects experiencing injection site reactions will be summarized by location and treatment group.

Erythema and swelling are recorded as size (in mm). The severity of these will be derived using the FDA guidance as below:

Erythema and Swelling Severity:

<2.5 cm	= None
2.5 to 5 cm	= Mild
5.1 to 10 cm	= Moderate
>10cm	= Severe.

The proportion of injections that resulted in reactions will also be summarized, by treatment group and all injection site reactions will be listed.

Any injection site reaction is also considered an adverse event of special interest and so the summaries of injection site reactions will be considered as part of the AESIs for the study.

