### 13.2. List of Tables

The columns Final and Admin Analysis identify the tables that will be produced for each of the Final Analysis and Administrative Interim Analysis, respectively.

Table Number	Table Title	Final	Admin Analysis
14.1.1	Subject Disposition – All Subjects	X	X
14.1.2	Demography and Baseline Characteristics – Safety Population	X	X
14.1.3	Medical History – Safety Population	X	
14.1.4.1	Concomitant Medications – Safety Population	X	
14.1.4.2	Background Asthma Medications – Safety Population	X	
14.1.5	Investigational Product Exposure – Safety Population	X	X
14.2.3.1.1	Biomarkers: Cytokines Change from Baseline Summary – Pharmacodynamic Population	X	X
14.2.3.1.2	Biomarkers: Cytokines Percentage Change from Baseline Summary – Pharmacodynamic Population	X	X
14.2.3.2.1.1	Biomarkers: Eosinophils Change from Baseline Summary – Pharmacodynamic Population	X	X
14.2.3.2.1.2	Biomarkers: Eosinophils Percentage Change from Baseline Summary – Pharmacodynamic Population	X	X
14.2.3.2.2.1	Biomarkers: Other Labs Change from Baseline Summary – Pharmacodynamic Population	X	X (IgE only)
14.2.3.2.2.2	Biomarkers: Other Labs Percentage Change from Baseline Summary – Pharmacodynamic Population	X	X (IgE only)
14.2.3.3.1	Biomarkers: Flow Cytometry Change from Baseline Summary – Pharmacodynamic Population	X	X
14.2.3.3.2	Biomarkers: Flow Cytometry Percentage of Baseline Summary – Pharmacodynamic Population	X	X
14.2.3.4.1.1	Biomarkers: FeNO Change from Baseline Summary – Pharmacodynamic Population	X	X
14.2.3.4.1.2	Biomarkers: FeNO Percentage Change from Baseline Summary – Pharmacodynamic Population	X	X

Table Number	Table Title	Final	Admin Analysis
14.2.3.4.2.1	Biomarkers: Other Spirometry Change from Baseline Summary – Pharmacodynamic Population	X	X (FEV1 only)
14.2.3.4.2.1	Biomarkers: Other Spirometry Percentage Change from Baseline Summary – Pharmacodynamic Population	X	X (FEV1 only)
14.2.4.1.1	CGI-C Summary – Safety Population	X	
14.2.4.1.2	CGI-C Categorical Summary – Safety Population	X	X
14.2.4.2.1	ACQ-7 Summary – Safety Population	X	X
Safety			
14.3.1.1	Injection Site Reactions Summary – Safety Population	X	X
14.3.1.2	Injection Site Reactions by Location – Safety Population	X	
14.3.1.3	Injection Site Reactions - Proportion with Reactions – Safety Population	X	
14.3.2.1.1	Overall Summary of Treatment Emergent Adverse Events up to Week 24 – Safety Population	X	

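### In Cohorts 1 and 2 the middle dose has fewer scheduled checks for injection site reactions than any other dose in Cohorts 1 to 4, and the SAP's per-injection proportion makes no allowance for this

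*SAP*

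**What the plan says.** **Analysis.** SAP 10.12.1 sets out several reaction summaries, one of which uses injections as the unit: "The proportion of injections that resulted in reactions will also be summarized, by treatment group and all injection site reactions will be listed". SAP 13.2 lists it as Table 14.3.1.3, "Injection Site Reactions - Proportion with Reactions", for the final analysis. Neither section mentions dose number or a rule for unequal checks. SAP 10.1.3 says placebo is generally pooled across cohorts, but allows it to be shown by dosing regimen in some summaries.

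**Doses.** Protocol 5.8.1: "Subjects in Cohorts 1 and 2 will receive 3 doses of study drug" and "Subjects enrolled in Cohort 3 will receive 2 doses of the study drug". Protocol 7.2.4 covers the single-dose cohort: "except for Cohort 4 where study drug will be administered on Day 1 ONLY".

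**Checks.** Protocol 3.3 has a row named "Assess injection site reactions" in each schedule.
- Table 5 (first dose, all cohorts) marks the first four visits, D1, D2, D4 and D8: "Assess injection site reactions X X X X".
- Table 6 (3-dose cohorts) has blacked-out cells, but their positions can be read. They fall on D29 and D36, then on D57, D58, D60 and D64.
- Table 8 (Cohort 3's second dose) has marks at D85, D86, D88 and D92.

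**Second route of capture.** Injection site reactions are adverse events of special interest, also captured by spontaneous reporting (Protocol 8.7). Adverse events are reviewed at every visit, including D36.

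**The concern.** A per-injection proportion is the natural way to compare tolerability between regimens with different numbers of doses, and Table 14.3.1.3 is the only reaction table whose title and text indicate that unit. The comparison is fair only if each injection has a similar chance of having a reaction recorded. One of the three doses in Cohorts 1 and 2 has half the scheduled checks of the others, and no visit is scheduled between D29 and D36. A reaction that starts after the dosing-day observation and clears before D36 can enter the count only through recall or spontaneous reporting, and the SAP does not say whether such a reaction counts.

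Safety and tolerability is the primary objective and the analysis is purely descriptive, so no model will adjust for the difference later. At stake is a reader concluding that the 3-dose regimens are better tolerated locally than the 2-dose or 1-dose regimens when part of the gap reflects how often people were examined.

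**Working it through.** The documents give no reaction rate, duration or recall rule, so there is no planned figure to reproduce. The check maps each schedule to days since dose and then bounds the effect.

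**Step 1. Checks in days since dose (nominal)**

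| Dose | Visit days | Days since dose |
|---|---|---|
| Dose 1, all cohorts (Table 5) | D1, D2, D4, D8 | 0, 1, 3, 7 |
| Dose 2, Cohorts 1–2 (Table 6) | D29, D36 | 0, 7 |
| Dose 3, Cohorts 1–2 (Table 6) | D57, D58, D60, D64 | 0, 1, 3, 7 |
| Dose 2, Cohort 3 (Table 8) | D85, D86, D88, D92 | 0, 1, 3, 7 |

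The windows are D29 ±2 and D36 ±1, so the second check can fall from 35 − 31 = 4 to 37 − 27 = 10 days after the middle dose.

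**Step 2. Direction.** The checks on days 0 and 7 are a subset of those on days 0, 1, 3 and 7. Under one recording rule, fewer checks cannot find more reactions.

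**Step 3. Size in Cohorts 1 and 2.** Let s be the chance of recording a reaction after the middle dose relative to the other doses. Assume equal true risk at each dose, equal injections per dose within a cohort, and all planned doses given. The middle dose is then 1/3 of injections, and

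observed / full-schedule proportion = (2 + s)/3.

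For placebo pooled over Cohorts 1 to 4 with two subjects per cohort, dosing occasions number 2 × (3 + 3 + 2 + 1) = 18, of which 4 are middle doses. The ratio per dosing occasion is (14 + 4s)/18.

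| s (assumed) | Cohorts 1–2 | Pooled placebo, by dosing occasion | Cohorts 3–4 |
|---|---|---|---|
| 1 | 1.00 | 1.00 | 1.00 |
| 0.9 | 0.97 | 0.98 | 1.00 |
| 0.75 | 0.92 | 0.94 | 1.00 |
| 0.5 | 0.83 | 0.89 | 1.00 |
| 0.25 | 0.75 | 0.83 | 1.00 |
| 0 (bound) | 0.67 | 0.78 | 1.00 |

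The row s = 0 means that no middle-dose reaction is recorded at all. It is a bound, since the dosing day and D36 are both checked.

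**Step 4. The placebo share is not fixed.** The SAP's denominator is injections, and injections per dose are redacted apart from the statement in Protocol 1.7 that Cohort 1 receives two per visit. If Cohorts 2, 3 and 4 receive a, b and c per dose, the middle-dose share of placebo injections is (2 + a)/(6 + 3a + 2b + c). With each between 1 and 3 (assumption), this runs from 3/18 = 17% (a = 1, b = c = 3) to 5/18 = 28% (a = 3, b = c = 1). The 4/18 = 22% behind the placebo column is one value in that range.

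**Step 5. Illustrative values of s.** A simulation assumed exponential onset (mean 0.1 to 2 days) and duration (mean 0.5 to 5 days), with a reaction counted only if present at a check and no recall. It gave s from 0.23 to 0.94, so a Cohort 1–2 ratio of 0.74 to 0.98. With full recall counted at D36, s = 1 and the ratio is 1.00.

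**Step 6. Scale in counts.** Cohort 1 plans 6 active subjects × 3 doses × 2 injections = 36 active injections, 12 of them at the middle dose. One missed reaction moves its proportion by 1/36 = 2.8 percentage points.

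**The case against.** The strongest reply is that no bias has been shown. An understatement needs reactions that begin after the dosing-day check, resolve before D36 and are not reported there. SAP 10.12.1 collects whether the subject experienced a reaction, which may include recall. Pain and tenderness need no measured size, and spontaneous reporting stays open throughout. This stands. A reader might infer that the Cohort 1 and 2 proportion is biased down by some stated percentage, but the documents support only unequal ascertainment with a known direction. The reply does not remove the point, because nothing says that a reaction recalled at D36 enters the per-injection numerator. The adverse event summaries count each preferred term once per subject (SAP 10.12.2), so they cannot rebuild a per-injection rate.

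Other points that stand:
- The shells in SAP Section 14 are not available, so the absence of rows by dose is inferred from the text of 10.12.1 and the table title.
- The dosing hold described in SAP 10.8 can move the middle-dose share away from one third. For a subject given only the first two doses it would be one half.
- Placebo subjects in Cohorts 1 and 2 follow the same schedule as their active counterparts. The imbalance against placebo arises only from pooling across cohorts.
- A reader might infer that severity is understated too. The SAP summarizes maximum severity per subject and symptom, so this is affected only where the worst reaction fell in the gap.
- The summary is descriptive, and no stopping rule in Protocol 5.9 uses it.

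**Conclusion.** The point holds as one of unequal ascertainment. In Cohorts 1 and 2 the middle dose, nominally one third of doses, has two scheduled checks against four for every other dose in Cohorts 1 to 4. The per-injection proportion as worded does not separate it. Comparisons with Cohorts 3 and 4, or with placebo pooled across cohorts, can only be tilted towards a lower figure in Cohorts 1 and 2.

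The relative understatement lies between 0% and about 33%. The upper limit assumes that all planned doses are given, true risk is equal across doses, and no middle-dose reaction is recorded. No value inside the range can be derived from the documents. The tilt against pooled placebo is smaller than against Cohorts 3 and 4, because pooled placebo also contains middle doses, and its exact size depends on redacted injection counts.

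A reader might also infer that middle-dose injections should be dropped from the overall proportion. That does not follow. It would discard about a third of the planned injection data in these cohorts, including reactions seen on D29 or D36, in a study whose objective concerns multiple doses.

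**What to change.** In SAP 10.12.1 and Table 14.3.1.3:

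1. Keep the overall proportion of injections with reactions, and add rows by dose number.
2. Add a between-group comparison on first-dose injections, which have the same D1, D2, D4 and D8 checks in every cohort.
3. Show placebo by dosing regimen beside pooled placebo. SAP 10.1.3 already permits this, and it gives Cohorts 1 and 2 a comparator on the same schedule.
4. Footnote that the middle dose in the 3-dose cohorts had fewer scheduled checks, nominally the dosing day and day 7, subject to visit windows.
5. State whether a reaction recalled at D36, but not present then, counts in the numerator.

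Label the rows by dose number rather than as first, middle and last, because with the dosing hold a subject's last dose received may have been the second.

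The change uses data already collected and needs no new visits. The cost is some SAP wording, extra table rows and smaller denominators per row (for Cohort 1 active, 12 injections per dose instead of 36 in total).

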### 10.12.2. *Adverse Events*

Adverse event (AE) data presentations will be produced for unsolicited adverse events that occur during the study.

All adverse events will be coded using MedDRA, Version 25.0.

Treatment emergent adverse events will be summarized over 2 distinct time periods within the study, from first dose of study treatment to Week 24, as well as from first dose of study treatment to Week 32 (i.e. over the entire study period).

Adverse events will be assigned to time periods according to the AE start and stop dates and times and dates/times of first dose of study treatment. Any adverse event with an onset date/time earlier than the date/time of first dose of study treatment will be classified as a pre-treatment adverse event. Any adverse event worsening in severity will be considered as a separate event, starting from the date/time of the updated severity.

Should any onset date for an adverse event be missing or only a partial date recorded (such that it cannot be determined if the event onset was prior to first dose of study treatment or not) then it will be assumed that the event is following first dose of study treatment, unless the adverse event stop date indicates otherwise.

If a subject experiences more than one adverse event with the same preferred term, that preferred term will be counted only once in summary presentations. It will be assigned the worst observed

severity and the strongest relationship to IMP among those events for the summaries in which those characteristics are considered.

Adverse Events of Special Interest (AESI) will be identified within the database as such. Additionally injection site reactions will be considered as AESIs.

An overall summary of adverse events will present the number of subjects with events and serious adverse events (also split by severity), number of subjects with adverse events and serious adverse events related to study treatment, the number of subjects with adverse events leading to discontinuation from study treatment or withdrawal from the study. This summary will be produced for adverse events occurring from first dose of study treatment to Week 24, and over the entire study period.

Additionally, each of the summaries below will be presented for the entire study period:

- Adverse Events by treatment group, System Organ Class (SOC) and Preferred Term (PT).
- Serious Adverse Events by treatment group, SOC and PT.
- Adverse Events by treatment group, SOC, PT and severity.
- Adverse Events related to study treatment by treatment group, SOC and PT.
- Adverse Events of Special Interest by treatment group, SOC and PT.

Listings will be provided for AEs, serious adverse events (SAEs), adverse events directly resulting in discontinuation of study treatment or withdrawal from study.

In all adverse event summary tables results will be displayed in descending order of the number of AEs across all active treatment groups by SOC and also preferred term within SOC.

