8.7 Adverse Events of Special Interest

Certain AEs have been identified as AEs of special interest (AESIs) due to the class of drugs being studied. These AEs will be captured through spontaneous reporting in the eCRF and the reporting of these AESIs will be described in the SAP. An AESI may be serious or non-serious. For this study, AESIs based on the class of drugs include:

- Allergic reactions.
- Immune complex disease.
- Severe infections which are defined as:
 - Life threatening or,
 - Requiring hospitalization or,
 - Requiring treatment with antiviral medications, IV antibiotics or medications for helminth parasitic infection or,
 - Requiring a permanent discontinuation of study drug.
- Injection site reactions.

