14.3.2.1.2	Treatment Emergent Adverse Events by System Organ Class and Preferred Term up to Week 24 – Safety Population	X	
14.3.2.1.3	Treatment Emergent Adverse Events by System Organ Class, Preferred Term and Severity up to Week 24 – Safety Population	X	
14.3.2.1.4	Treatment Emergent Adverse Events Related to IMP by System Organ Class and Preferred Term up to Week 24 – Safety Population	X	
14.3.2.1.5	Treatment Emergent Adverse Events of Special Interest by System Organ Class and Preferred Term up to Week 24 – Safety Population	X	
14.3.2.1.6	Treatment Emergent Serious Adverse Events by System Organ Class and Preferred Term up to Week 24 – Safety Population	X	X
14.3.2.1.7	Treatment Emergent Adverse Events Leading to Discontinuation of Investigational Product by System Organ Class and Preferred Term up to Week 24 – Safety Population	X	

Table Number	Table Title	Final	Admin Analysis
14.3.2.1.8	Treatment Emergent Adverse Events Leading to Withdrawal from the Study by System Organ Class and Preferred Term up to Week 24 – Safety Population	X	X
14.3.2.2.1	Overall Summary of Treatment Emergent Adverse Events Over Entire Study Period – Safety Population	X	
14.3.2.2.2	Treatment Emergent Adverse Events by System Organ Class and Preferred Term Over Entire Study Period – Safety Population	X	
14.3.2.2.3	Treatment Emergent Adverse Events by System Organ Class, Preferred Term and Severity Over Entire Study Period – Safety Population	X	
14.3.2.2.4	Treatment Emergent Adverse Events Related to IMP by System Organ Class and Preferred Term Over Entire Study Period – Safety Population	X	
14.3.2.2.5	Treatment Emergent Adverse Events of Special Interest by System Organ Class and Preferred Term Over Entire Study Period – Safety Population	X	
14.3.2.2.6	Treatment Emergent Serious Adverse Events by System Organ Class and Preferred Term Over Entire Study Period – Safety Population	X	
14.3.3.1	Haematology Parameters Summary – Safety Population	X	
14.3.3.2	Haematology Parameters: Shift of Normal Range – Safety Population	X	
14.3.4.1	Biochemistry Parameters Summary – Safety Population	X	
14.3.4.2	Biochemistry Parameters: Shift of Normal Range – Safety Population	X	
14.3.5.1	Coagulation Parameters Summary – Safety Population	X	
14.3.5.2	Coagulation Parameters: Shift of Normal Range – Safety Population	X	
14.3.6	Urinalysis Parameters: Summary – Safety Population	X	
14.3.7	Vital Signs Parameters Summary – Safety Population	X	

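### No by-arm count of distinct subjects is planned for three of the protocol's four AESI categories

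*SAP*

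**What the plan says.** Protocol 8.7 introduces its list with "For this study, AESIs based on the class of drugs include" and gives four categories: allergic reactions, immune complex disease, severe infections and injection site reactions. The third is a composite. It opens with "Severe infections which are defined as" and gives four alternative criteria: threat to life, admission to hospital, certain anti-infective treatments, or permanent stopping of study drug. The same section states that "the reporting of these AESIs will be described in the SAP".

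SAP 10.12.2 takes this up in three places:

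- Identification: "Adverse Events of Special Interest (AESI) will be identified within the database as such". No category variable is described.
- Injection site reactions: "Additionally injection site reactions will be considered as AESIs".
- Tabulation: "Adverse Events of Special Interest by treatment group, SOC and PT", for the entire study period. SAP 13.2 adds a version to Week 24, Table 14.3.2.1.5, titled "Treatment Emergent Adverse Events of Special Interest by System Organ Class and Preferred Term up to Week 24". Table 14.3.2.2.5 covers the entire study.

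The counting rule in SAP 10.12.2 is that a subject with several events under one preferred term is counted once for that term. The overall adverse event summary described there names no AESI item. SAP 13.4 lists no separate AESI listing. Injection site reactions have Tables 14.3.1.1 to 14.3.1.3.

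**The concern.** The four categories are clinical groupings that the protocol singles out as class risks, and safety is the primary objective. For each category, a reader of the report will want to know how many subjects in each arm were affected. A table built on system organ class (SOC) and preferred term (PT) answers a different question, because it removes duplicate subjects within a term and not across the terms that make up a category.

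With 6 active subjects per cohort, a few related events coded to different terms would appear as scattered rows of one subject each, and a pattern could be overlooked. If the grouping is done only when the report is written, it will be done with allocations known and without a prespecified rule.

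**Working it through.** The plan gives no figure to reproduce. The check compares what each document provides per category and then asks how much an SOC/PT table can say about a category.

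**Side by side**

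| Protocol 8.7 category | By-arm subject count in the SAP |
|---|---|
| Allergic reactions | By PT within SOC only (14.3.2.1.5, 14.3.2.2.5) |
| Immune complex disease | By PT within SOC only (same tables) |
| Severe infections | By PT within SOC only (same tables) |
| Injection site reactions | Own tables (14.3.1.1 to 14.3.1.3) |

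**What PT counts imply for a category**

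Suppose a category is made up of preferred terms with n1, n2, …, nk subjects in an arm of size N. The number D of distinct subjects in the category satisfies

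max(nj) ≤ D ≤ min(n1 + … + nk, N).

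N = 6 comes from the protocol (section 3.1.1: 6 active and 2 placebo per cohort). The event counts below are assumed.

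- Terms with 3, 2 and 1 subjects: the maximum is 3, the sum is 3 + 2 + 1 = 6, and min(6, 6) = 6. D lies between 3/6 (50%) and 6/6 (100%).
- Three terms with 1 subject each: the maximum is 1, the sum is 3, and min(3, 6) = 3. D lies between 1/6 (17%) and 3/6 (50%).
- One term only: the two bounds coincide, so the table gives D exactly.

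The table therefore fixes the category count when one term makes up the category, and otherwise gives only a range.

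**Where the gap is widest**

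Allergic reactions can be coded, for example, as urticaria, bronchospasm or hypersensitivity, which belong to the skin, respiratory and immune classes. Protocol 8.9 itself cites allergic bronchospasm as an example of an important medical event. An SOC subtotal would not gather such terms.

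Severe infections are different. Only flagged events enter the AESI tables, so if the flag follows Protocol 8.7, an infection row there already holds severe infections. If those events code to one SOC and the shells show subject counts at SOC level (both assumptions), that row is close to the category count.

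**Are injection site reactions in these tables?**

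SAP 10.12.1 treats the separate injection site summaries as belonging to the AESI reporting. SAP 10.12.2 confines adverse event presentations to unsolicited events, yet also classes injection site reactions as AESIs. The text does not settle whether they appear in Tables 14.3.2.1.5 and 14.3.2.2.5.

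**The case against.** The strongest reply is that nothing in the protocol is breached. Section 8.7 hands AESI reporting to the SAP and does not ask for category totals, and SOC/PT is a conventional layout. The study is descriptive, with 24 to 40 subjects, and Listing 16.2.7.2 shows every adverse event, so category counts can be rebuilt by hand. The shells in SAP Section 14 are not in the public text and might contain category rows.

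Much of this stands, and it keeps the point small. Two parts do not fully answer it. The table titles and SAP 10.12.2 both specify SOC and PT, so category rows in the shells cannot be ruled out but are not indicated. Rebuilding from listings is feasible, but it would be done after unblinding and without an agreed grouping.

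A reader might also infer more than the documents support:

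- That subjects with these events are never counted by arm. They are, by preferred term, in two tables. Some severe infections would also reach other by-arm tables: those meeting seriousness criteria in 14.3.2.1.6 and 14.3.2.2.6, and those leading to discontinuation up to Week 24 in 14.3.2.1.7.
- That the SAP errs by counting injection site reactions as AESIs. The protocol lists them as such, and they have their own tables.
- That injection site reactions will mask a difference in an overall AESI count. No available text plans such a total, and Protocol 1.7 reports none of these reactions after the earlier subcutaneous dose.

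**Conclusion.** The point holds in a limited form. For allergic reactions, immune complex disease and severe infections, the available text plans no distinct-subject count per category by arm. The loss of information is real when a category spans several terms: in the assumed examples with N = 6, the count is known only to within 3/6 to 6/6, or 1/6 to 3/6. It is greatest for allergic reactions and may be slight for severe infections.

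The conclusion assumes that the shells follow the table titles and that no category variable is defined elsewhere. Severity is minor: no estimate or planned inference changes, but the improvement is cheap and bears on the primary safety objective.

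**What to change.** 1. Add a variable to each AESI record giving its Protocol 8.7 category. Assign it at the blinded data review meeting already planned before database lock (SAP sections 4, 9 and 10.3), and record the rule used. Check severe infections against the seriousness, concomitant medication and action-taken fields already collected.
2. Make category the first level of Tables 14.3.2.1.5 and 14.3.2.2.5. Show distinct subjects (n, %) by treatment group and pooled placebo, with PT nested within category.
3. State whether injection site reactions enter these tables. If they do, show them on a separate row and add a line for any AESI excluding injection site reactions.

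The cost is one derived variable for what is likely to be a small number of events, a short item at a meeting already scheduled, and two revised shells. No new data are needed.
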